3.2.1 Dose Limiting Toxicity

Toxicity should be evaluated and defined according to CTCAE version 5.0, and should only include events assessed as related to talimogene laherparepvec during treatment and up to 30 days after the last talimogene laherparepvec injection.

The following herpetic events should be considered as DLTs:

- Serious herpetic events such as herpetic encephalitis, encephalomyelitis or disseminated hepatic infection.
- Any herpetic events confirmed due to talimogene laherparepvec that require treatment with acyclovir or similar anti-viral agent. Talimogene laherparepvec treatment should be suspended if treatment is required with systemic acyclovir or other anti-virals. If ongoing anti-viral treatment is required, talimogene laherparepvec treatment should be permanently discontinued.

The following are also considered DLTs:

- Grade 3 or greater immune-mediated adverse events.
- Any grade plasmacytoma at or near the injection site or evidence of impaired wound healing at the injection site.
- Grade 3 or greater allergic reactions considered at least possibly related to talimogene laherparepvec.
- Grade 4 non-hematologic toxicity.
- Grade 3 non-hematologic toxicity lasting > 3 days despite optimal supportive care;
 - Grade 3 fatigue will not be classified as DLT, irrespective of duration.
- Any Grade 3 or higher non-hematologic laboratory value if:
 - Medical intervention is required, or
 - The abnormality leads to hospitalization, or
 - The abnormality persists for > 1 week unless deemed not clinically important per both treating physician and study PI or co-PI.
- Grade 3 or 4 febrile neutropenia.
- Grade 4 thrombocytopenia associated with bleeding event required intervention.
- Any other intolerable toxicity leading to permanent discontinuation of talimogene laherparepvec.
- Grade 5 toxicity (i.e., death).

If an unexpected DLT occurs, talimogene laherparepvec administration should be delayed until the DLT has resolved to at least CTCAE (v. 5.0) Grade 1. If talimogene laherparepvec dosing is delayed by more than 6 weeks from the date of the planned dose due to the occurrence of an adverse event that is

considered related to talimogene laherparepvec, the subject must be permanently taken off talimogene laherparepvec treatment.

Management and dose modifications associated with all adverse events are outlined in Section 7.0.

3.3 Dose Expansion Cohort

Once the MTD has been determined, an additional 6 subjects will be enrolled to the dose expansion cohort. All subjects will receive an initial seroconversion dose of talimogene laherparepvec 4×10^6 PFU on Cycle 1 Day 1. Three weeks (+3 days) after the initial seroconversion dose, patients will receive talimogene laherparepvec at the MTD every 2 weeks (± 3 days) for up to 4 doses (in addition to the initial seroconversion dose, which all patients will receive). The length of the first cycle is 5 weeks and the subsequent cycles are 2 weeks in duration. There are a total of four cycles.

4.0 SUBJECT SELECTION

4.1 Inclusion Criteria

1. Patients must have stage IV peritoneal surface dissemination of gastrointestinal cancer or recurrent ovarian, fallopian tube or primary peritoneal cancer with metastatic disease to the peritoneum that cannot be completely resected at time of abdominal exploration. Please note:
 - a. Locoregional extension of peritoneal disease beyond the peritoneal cavity (including but not limited to the pleura and subcutaneous soft tissue) is permitted with PI approval,
 - b. Radiographically measurable disease per RECIST 1.1 is preferable, but for patients with previously documented gastrointestinal, fallopian tube, ovarian, or primary peritoneal cancer, for whom relevant tumor markers (including but not limited to CEA, CA 19-9 or CA-125) have been useful markers of disease progression and/or response to treatment, an elevated relevant tumor marker (including but not limited to CEA, CA 19-9 or CA-125) above the institutional upper limit of normal could be substituted for radiographic imaging,
 - c. Asymptomatic primary tumors are permitted.
2. Subjects must have had at least one prior round of systemic therapy in the metastatic setting or have refused or be ineligible for standard systemic therapy for their disease type. No prior systemic therapy is required for low grade mucinous cancers.
3. Age ≥ 18 years
4. ECOG Performance Score of 0-2
5. Adequate marrow function as evidenced by:
 - a. Absolute neutrophil count (ANC) $\geq 1,500/\mu\text{L}$
 - b. Platelets $\geq 100,000/\mu\text{L}$
 - c. Hemoglobin (Hgb) $\geq 8 \text{ g/dL}$
6. Adequate renal function as evidenced by serum creatinine $\leq 1.5 \times$ upper limit of normal (ULN), OR 24-hour creatinine clearance $\geq 60 \text{ mL/min}$ for subject with creatinine levels $> 1.5 \times$ ULN.
7. Adequate hepatic function as evidenced by:
 - a. Serum bilirubin $\leq 1.5 \times$ ULN OR direct bilirubin \leq ULN for a subject with total bilirubin level $> 1.5 \times$ ULN
 - b. Aspartate aminotransferase (AST) $\leq 3 \times$ ULN
 - c. Alanine aminotransferase (ALT) $\leq 3 \times$ ULN
 - d. Alkaline phosphatase $\leq 3 \times$ ULN
8. INR or PT $\leq 1.5 \times$ ULN, unless the subject is receiving anticoagulant therapy, in which case PT and PTT/aPTT must be within therapeutic range of intended use of anticoagulants (and may need to be held per institutional standards for placement of the Bard peritoneal catheter).

9. Patients must be recovered from both acute and late effects of any prior surgery, radiotherapy or other antineoplastic therapy.
10. Patients of reproductive potential (men and women) must agree to use medically accepted barrier methods of contraception (e.g., male or female condom) at the time of pregnancy test (women of childbearing potential only), during the course of the study and for 90 days after the last dose of study drug, even if oral contraceptives are also used. All subjects of reproductive potential must agree to use both a barrier method and a second method of birth control during the course of study and for 90 days after the last dose of study drug.
11. Patients or their legal representatives must be able to read, understand and provide informed consent to participate in the trial.

4.2 Exclusion Criteria

1. Prior chemotherapy, radiotherapy, biological cancer therapy, targeted therapy, or major surgery within 28 days prior to enrollment or has not recovered to CTCAE grade 1 or better from adverse event due to cancer therapy administered more than 28 days prior to enrollment. (Exception: Patients with peripheral neuropathy < Grade 3 are eligible)
2. Patients who received radiotherapy to more than 25% of their bone marrow.
3. Currently receiving treatment with another investigational device or drug study, or < 30 days since ending treatment with another investigational device or drug study(s). Other investigational procedures while participating in this study are excluded.
4. Known active central nervous system (CNS) metastases. Subjects with previously treated brain metastases may participate provided they are stable (without evidence of progression by imaging for at least four weeks prior to the first dose of trial treatment and any neurologic symptoms have returned to baseline), have no evidence of new or enlarging brain metastases, and are not using steroids >10 mg/day of prednisone or equivalent. The exception does not include carcinomatous meningitis, which is excluded regardless of clinical stability.
5. Metastatic disease in a site other than the peritoneal surfaces. Note: Locoregional extension of peritoneal disease may be permitted with PI approval.
6. History or evidence of active autoimmune disease for which subject currently requires systemic treatment (i.e., with use of disease modifying agents, corticosteroids, or immunosuppressive drugs). Replacement therapy (e.g., thyroxine, insulin, or physiologic corticosteroid replacement therapy for adrenal or pituitary insufficiency, etc.) is not considered a form of systemic treatment.
7. Evidence of clinically significant immunosuppression such as the following:
 - a. Primary immunodeficiency state such as Severe Combined Immunodeficiency Disease.
 - b. Concurrent opportunistic infection.
 - c. Receiving systemic immunosuppressive therapy (> 2 weeks) including oral steroid doses >10mg/day of prednisone or equivalent within 7 days prior to enrollment.
8. History of allogenic organ or hematopoietic transplant.
9. Active HSV that requires intermittent or chronic systemic anti-herpetic therapy or prior complications of herpetic infection, e.g. herpetic keratitis or encephalitis.
10. Requiring intermittent or chronic systemic (intravenous or oral) treatment with an antiherpetic drug (e.g., acyclovir), other than intermittent topical use.
11. Prior treatment with talimogene laherparepvec or any other oncolytic virus.

12. Subject has known sensitivity to talimogene laherparepvec or any of its components to be administered during dosing.
13. Prior therapy with tumor vaccine.
14. Receipt of a live vaccine within 28 days prior to enrollment.
15. Known to have acute or chronic active hepatitis B or C infection (active, previously treated, or both).
16. Known history of HIV infection.
17. Active infection or fever $\geq 101.3^{\circ}\text{F}$.within 3 days of port placement. .
18. Bleeding disorders that would preclude intraperitoneal port placement.
19. Refractory ascites that requires palliative paracentesis more frequently than once a month. Any other medical condition, including mental illness or substance abuse, deemed by the Investigator to be likely to interfere with a patient's ability to sign informed consent, cooperate and participate in the study or interferes with the interpretation of the results.
20. History of other malignancy within the past 5 years.
21. Female subjects who are pregnant or breast-feeding, or planning to become pregnant during study treatment or through 90 days after the last dose of talimogene laherparepvec.
22. Subjects of childbearing potential who are unwilling to use acceptable method(s) of effective contraception during study treatment and through 90 days after the last dose of talimogene laherparepvec.
23. Sexually active subjects and their partners unwilling to use male or female latex condom to avoid potential viral transmission during sexual contact while on treatment and within 90 days after treatment with talimogene laherparepvec.

4.3 Inclusion of Women and Minorities

Men and women of all races and ethnic groups are eligible for this trial.

5.0 STUDY ASSESSMENTS

Note: After Cycle 1, if the subject is unable to have a study assessment taken within the defined time window due to an event outside of his or her control (e.g., clinic closure, personal emergency, inclement weather, vacation), the assessment should be performed as close as possible to the required schedule.

Refer to **Appendix C for Study Calendar**.

5.1 Screening Period

During the Screening Period, subjects are consented and screened for the study. Informed consent must be obtained before initiation of any screening procedure that is performed solely for the purpose of determining eligibility for this study. Evaluations performed as part of routine care before informed consent can be considered as screening evaluations if done within the defined screening period, and if permitted by the local Institutional Review Board (IRB) / Independent Ethics Committee (IEC) policies. Study eligibility is based on meeting all of the inclusion criteria and none of the exclusion criteria (refer to [Section 4.0](#)) before the first dose of study drug on Cycle 1 Day 1.

The following study procedures must be done within 28 days prior to Cycle 1 Day 1:

- Demographics
- Medical and cancer history
- Concomitant medications
- Physical examination
- Abdominal measurement
- Height
- Vital signs and weight
- ECOG performance status
- Adverse event assessment (review of baseline symptoms)
- Tumor assessment (CT and/or MRI scans)
- Blood tumor marker, if clinically indicated (e.g., CEA or CA19-9)
- Whole blood (for pharmacogenomics) (may be collected pre-dose on Cycle 1 Day 1)
- Coagulation tests (must be done prior to catheter placement)
- Peritoneal catheter placement (must be placed after confirmation of eligibility)

The following study procedures must be done within 7 days prior to Cycle 1 Day 1:

- CBC with differential
- Chemistries including liver function tests (LFTs)
- Serum pregnancy test (only for women of childbearing potential)

Subject eligibility is determined using lab results obtained prior to peritoneal port placement and up to 7 days prior to Cycle 1 Day 1. The Screening Period ends upon placement of the peritoneal port or final determination that the subject is ineligible for the study. Patients with pre-existing peritoneal ports for standard of care treatment are eligible for participation. For these patients the Screening Period ends upon receipt of the first dose of study drug or final determination that the subject is ineligible for the study.

5.2 Peritoneal Catheter Placement

After confirmation of patient eligibility, the peritoneal catheter must be placed prior to initiation of treatment. Catheter placement must occur on Day -4 (+/- 2 days) prior to C1D1.

5.3 Treatment Period

During the Treatment Period, subjects will receive an initial seroconversion dose of talimogene laherparepvec on Day 1 of Cycle 1. Three weeks (± 3 days) after the initial seroconversion dose, patients will receive talimogene laherparepvec at their designated dose level every 2 weeks (± 3 days) for up to four doses or until either: 1) the occurrence of unacceptable treatment-related toxicity; or 2) other reason(s) for subject discontinuation as described in [Section 5.7](#).

All subjects will have study procedures weekly during the first cycle, then Day 1 of each cycle. After the completion of the first cycle, laboratory assessments may be obtained up to 3 days prior to Day 1. If clinically indicated, additional visits and/or safety assessments may be warranted.

The following study procedures must be completed on Day 1 of each cycle:

- Physical examination
- Abdominal measurement
- Vital signs (q15 min x 1 hour and again after additional hour of observation)

- Weight
- Concomitant medications
- ECOG performance status
- Adverse event assessment
- CBC with differential (results from eligibility review on day -7 to -3 should be used for C1D1)
- Chemistries including LFTs (results from eligibility review on day -7 to -3 should be used for C1D1)
- Viral load (prior to treatment D1 of each cycle)
- Urine pregnancy test prior to each treatment (only for women of childbearing potential)
- Peritoneal Cytokines (prior to treatment on C2D1 and C4D1)
- Immune cells (prior to treatment on C2D1 and C4D1)
- Plasma (prior to treatment D1 of each cycle)

The following study procedures must be completed on **Days 8, 15 and 29 of Cycle 1:**

- Physical examination
- Vital signs and weight
- Concomitant medications
- ECOG performance status
- Adverse event assessment
- CBC with differential
- Chemistries including LFTs
- Viral load

The following study procedures must be completed **on Cycle 1 Day 22:**

- Physical examination
- Vital signs (q15 min x 1 hour and again after additional hour of observation)
- Weight
- ECOG performance status
- CBC with differential
- Chemistries including LFTs
- Viral load (prior to treatment)
- Plasma (prior to treatment)

The following study procedures must be completed **at C4D1 (+/-3 days):**

- Concomitant medications
- Adverse event assessments
- Peritoneal cytokines (prior to treatment)
- Immune cells (prior to treatment)
- Plasma
- Viral load (prior to treatment)

The following study procedures must be completed **at C4D14 (+/-3 days):**

- Tumor assessment (CT and/or MRI scans)
- Blood tumor marker, if clinically indicated (e.g., CEA or CA19-9)

Restaging scans will be performed at C4D14 (+/- 3 days) on study treatment and disease response will be assessed using guidelines described in [Section 5.6](#).

The Treatment Period ends when a subject receives his or her last dose of study treatment; the subject then enters the Follow-up Period.

5.4 Follow-up Period

Subjects should return 30 (± 7) days after their last dose of study drug for an off-treatment visit to complete the following study procedures:

- Physical examination
- Abdominal measurement
- Vital signs and weight
- Concomitant medications
- ECOG performance status
- Adverse event assessment
- CBC with differential
- Chemistries including LFTs
- Serum pregnancy test (only for women of childbearing potential)
- Viral load (at disease progression and 30 day off treatment follow up)
- Peritoneal cytokines (at disease progression or off treatment, and 30 day off treatment follow up)
- Immune cells (at disease progression or off treatment, and 30 day off treatment follow up)
- Plasma (at disease progression or off treatment)

At the time of the follow up visit, the treating physician can determine whether or not to remove the IP catheter. If they anticipate using it for other IP therapies, it can be left in. If catheter is removed, treating physician may also determine whether it is clinically indicated to do PT/PTT. Additional follow-up may occur for subjects with adverse events (AEs) related to study drug that are ongoing at the time of this off-treatment visit unless AE is deemed unresolvable or subject has started a new anti-cancer treatment regimen.

For long-term follow up, subjects will be followed for progression every 12 weeks or as indicated until disease progression or start of new anti-cancer therapy. For subjects that complete or discontinue treatment without documented disease progression, subjects will have disease status (blood tumor marker(s) and restaging scans with RECIST 1.1 evaluation every 12 weeks) followed until disease progression or start of new anti-cancer treatment regimen.

All subjects will be followed for survival for up to 1 year after completing treatment. Survival status may be collected by personal interviews or review of medical records.

5.5 Laboratory Assessments

Local laboratories will perform all clinical laboratory tests using standard procedures, and results will be provided to the Investigator. Abnormalities in clinical laboratory tests that lead to a change in subject management (e.g., requirement for additional medication, treatment or monitoring) are considered clinically significant for the purposes of this study, and will be recorded on the case report form (CRF). If laboratory values constitute part of an event that meets criteria defining it as serious, the event (and associated laboratory values) must be reported as a serious adverse event (SAE).

Refer to [Appendix D](#) for details of laboratory tests for this study. In addition, blood tumor markers (if clinically indicated) such as CEA and/or CA19-9, will be obtained at baseline and at every restaging.

5.6 Adverse Event Assessment

AE definition is described in [Section 10.1](#). AEs will be documented throughout the study. AE seriousness, grade, and relationship to study drug will be assessed by the Investigator using NCI-CTCAE version 5.0

(https://ctep.cancer.gov/protocolDevelopment/electronic_applications/docs/CTCAE_v5_Quick_Referee_5x7.pdf).

SAE definitions and reporting requirements are described in [Section 10.2](#).

Select non-serious and serious adverse events also known as Events of Clinical Interest (ECI) must be recorded and reported as described in [Section 10.3](#).

5.7 Tumor Assessments

Tumor Response will be assessed via a composite of a variety of endpoints and ultimately, the treating physician's judgment and assessment of these endpoints. Given the variability in clinical presentation of these malignancies, radiographic imaging findings, and baseline laboratory values, assessing tumor response may take into account clinical features, radiographic response, laboratory response, and clinical endpoints.

Clinical features may include, but are not limited to, performance status (ECOG or Karnofsky score), abdominal girth, development of bowel obstructions felt to be resulting from peritoneal tumor deposits, development of clinically-evident ascites, and frequency of paracenteses due to malignant ascites.

Radiographic response may be used to track those patients who have radiographically-evaluable tumor deposits at baseline, which may be prone to following with serial imaging. For a subset of these patients who have such radiographically-evaluable lesions, it may be possible to assess tumor response based on serial imaging (CT chest/abdomen/pelvis with and without contrast and/or MRI or PET imaging), using RECIST version 1.1 criteria. Some peritoneal surface malignancies will not be amenable to grading using RECIST version 1.1 criteria. However, there are other imaging scoring systems such as the SPAAT[11] Score or a modified peritoneal cancer index based upon multi-detector CT imaging [12] which may be helpful in establishing a radiographic determination of tumor response to therapy. The exact method of analyzing a given patient's imaging will depend on that patient's radiographic findings at baseline, and the radiologist's determination of the best method of following serial changes in imaging.

For those patients who have elevated blood tumor markers at baseline, following the response of these tumor markers to therapy will factor into assessing tumor response to therapy.

Clinical endpoints of progression-free survival and overall survival will also be used to assess response to therapy.

Given the heterogeneity in presentations of patients with peritoneal surface malignancies, patients will likely be followed by a composite of a variety of the above endpoints, and these endpoints may be different from patient to patient. However, for a given patient, all attempts will be made to use the same method for tumor assessment at every assessment timepoint. Progressive disease (PD) may manifest in findings such as significant clinical progression, evidence of 20% increase in disease seen on

imaging, and/or increase in tumor marker by 20% over baseline. Response may manifest in findings such as improvement in clinical symptoms, evidence of 30% decrease in measurable tumor burden, and/or 30% decrease in tumor marker from baseline.

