All patients will receive an initial seroconversion dose of intraperitoneal talimogene laherparepvec 4×10^6 PFU on Cycle 1 Day 1 to enable seroconversion as described in the currently approved treatment protocol for the treatment of cutaneous melanoma. Three weeks after the initial seroconversion dose, patients will receive talimogene laherparepvec at the dose level for the cohort for which they are enrolled every 2 weeks for up to 4 doses (in addition to the initial seroconversion dose, which all patients will receive). The length of the first cycle is 5 weeks and subsequent cycles are 2 weeks in duration.

In the Dose Escalation Cohort, three subjects will be enrolled at the starting dose of 4×10^6 PFU, and the dosing will continue in the standard '3+3' dose escalation scheme. If the starting dose is tolerated, enrollment will continue at 4×10^7 and 4×10^8 PFU. Once the MTD is determined, six subjects will be enrolled to the Dose Expansion Cohort at the MTD. All subjects will be dosed with talimogene laherparepvec IP once every 2 weeks for up to 4 doses (in addition to the initial seroconversion dose, which all patients will receive).

Study Assessments

Safety: Toxicity and safety assessments will be performed weekly during the 5 weeks, then every 2 weeks for up to 4 treatment visits. These assessments will include vital signs, ECOG performance status, medical history, physical examination, complete blood count (CBC), biochemistry, creatinine, AST, ALT, and bilirubin. Toxicities will be recorded using National Cancer Institute Common Terminology Criteria for Adverse Events (NCI-CTCAE) version 5.0. General symptom management and supportive care will be provided as clinically indicated to ensure optimal patient care. After discontinuation of study treatment, subjects will have toxicity and safety assessments 30 days after last dose of study drug.

Tumor Assessments

Restaging scans and blood tumor markers will be repeated at the end of cycle 4, after receipt of the fifth dose of study drug. Tumor response will be assessed using treating physician's discretion, based on a composite of RECIST 1.1 measurements, blood tumor markers (CEA or CA-125), measurements of abdominal girth, and/or clinical response.

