1.0 INTRODUCTION

1.1 Background

Peritoneal carcinomatosis (PC) represents a widespread metastatic dissemination throughout the abdomen and pelvis of many organ-based malignancies. Cancers of the ovary, colon, stomach, and appendix are common primary tumor sites that give rise to PC[1]. There are approximately 22,000 new cases of epithelial ovarian cancer in the United States in 2014. Because 70% of patients with ovarian cancer present with advanced stage disease[1], epithelial ovarian cancer is the leading cause of gynecologic cancer death at 14,000 deaths each year. Fallopian tube carcinoma is a rare gynecological cancer with approximately 300-400 new cases annually. It is often included as a subset of epithelial ovarian cancer, along with primary peritoneal cancer, as the clinical course and treatment of these three cancers are the same [21]. Recent literature suggests that some high-grade serous ovarian cancer (HGSOC) originates in the fallopian tube [21,22]. Similarly, colon cancer presents with metastases to the peritoneum in up to 15% of patients at the time of diagnosis[2], and in patients treated curatively, PC is involved at recurrence in up to 50% of patients[1]. PC from gastric cancer is discovered at the time of initial surgery in 10-20% of patients and in up to 60% of patients who have undergone a curative resection for T3/T4 tumors[3]. Although the incidence of appendiceal cancer is only between 0.1-1 in 1,000,000 people annually, patients are usually asymptomatic until aggressive PC has been established[4]. Unfortunately, PC is uniformly a terminal disease with a median survival of six months[3]. Systemic chemotherapy is palliative and generally provides limited improvement in survival[1]. Intraperitoneal therapy provides a pharmacokinetic advantage in the treatment of local regional disease relative to systemic therapy due to the peritoneal-plasma partition[5].

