9.1.4 Exploratory Endpoints

In addition to defining the MTD, the study will provide useful preliminary data concerning efficacy. Methods of assessing response will be specific to each individual patient as described in Section 5.6. In the subset of patients with radiographically measurable disease RECIST 1.1 criteria will be used.

Patients in the per protocol population will be classified as responder or non-responder and the proportion of patients exhibiting response at trial closure by any criteria will be estimated by the 90% confidence interval. Patients who experience a radiographic/tumor marker CR will undergo confirmatory laparoscopy.

Time to progression measured from study entry to documented progression of disease will be estimated by the method of Kaplan-Meier in the intent-to-treat population. Patients who withdraw from the trial prior to disease progression, are either lost to follow-up, die or begin alternative treatments prior to progression, will be censored at the date considered to be lost to follow-up, date of death, or the first day of alternative therapy.

For all efficacy endpoints, analyses will be performed overall and in the patients treated at the MTD. These analyses are primarily exploratory since the data will be from only a limited number of patients available for the study.

As a first approach to addressing our exploratory aim of evaluating changes in peritoneal cavity leukocyte populations after the treatment of peritoneal surface dissemination of gastrointestinal, fallopian tube, ovarian, and primary peritoneal cancers with talimogene laherparepvec, we will perform multi-color flow cytometry analysis on peritoneal lavage fluid from patients at baseline (prior to seroconversion dose on C1D1), prior to treatment on C2D1, and on C4D1. If the subject comes off treatment mid cycle, there will be an additional plasma sample at the time of disease progression or off treatment. Immune cells will be stained with fluorescent antibodies specific for markers of major leukocyte subsets as commonly performed by the [name] Lab.

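### Section 5.7 lists PFS and OS among the inputs to the physician-judged tumour response, unlike the synopsis, and 9.1.4 does not keep survival or non-progression out of the response proportion

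*Combined protocol and SAP*

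**What the plan says.** Section 5.7 opens by leaving the judgement to the physician: "Tumor Response will be assessed via a composite of a variety of endpoints and ultimately, the treating physician's judgment and assessment of these endpoints". It then lists what may enter that judgement: "assessing tumor response may take into account clinical features, radiographic response, laboratory response, and clinical endpoints". Each category is explained in turn, and the last is explained as follows: "Clinical endpoints of progression-free survival and overall survival will also be used to assess response to therapy". No length of PFS or OS, and no assessment time, is attached.

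The same section later gives examples of response: "Response may manifest in findings such as improvement in clinical symptoms, evidence of 30% decrease in measurable tumor burden, and/or 30% decrease in tumor marker". Survival and absence of progression are not among them, but the list is open.

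The synopsis, under Tumor Assessments, describes the judgement as "based on a composite of RECIST 1.1 measurements, blood tumor markers (CEA or CA-125), measurements of abdominal girth, and/or clinical response". PFS and OS do not appear there.

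Section 9.1.4 makes each per protocol patient a responder or non-responder, and says that "the proportion of patients exhibiting response at trial closure by any criteria will be estimated by the 90% confidence interval". It also says: "In the subset of patients with radiographically measurable disease RECIST 1.1 criteria will be used". For the method of assessing response it points to Section 5.6, which covers adverse events; the method is in 5.7.

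**The concern.** Response in a single patient should mean a change in that patient's disease. Being alive, or not yet progressed, is a state that many patients would be in without an active drug, and this trial has no control arm to show how many. Section 5.7 nevertheless places PFS and OS alongside imaging, markers and clinical features as material for the response judgement, with no threshold. Section 9.1.4 then accepts response under any criterion.

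At stake is the meaning of the response proportion and its 90% interval. If some physicians give weight to survival or non-progression, the proportion partly reflects prognosis and cannot be compared with a RECIST-based rate. The scope is widest where RECIST does not apply: inclusion criterion 1b admits patients on an elevated tumour marker in place of measurable disease. Tightening how scans and markers are combined would not cure this, because PFS and OS would still be inputs.

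**Working it through.** **The passages side by side**

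| Place | Inputs to response | PFS/OS included? |
|---|---|---|
| Synopsis, Tumor Assessments | RECIST 1.1, markers, girth, clinical response | No |
| 5.7, list of inputs and the sentence explaining it | Clinical features, radiographic, laboratory, clinical endpoints | Yes, by name |
| 5.7, examples of response | Better symptoms, 30% fall in tumour burden, 30% fall in marker | No, but the list is open |
| 9.1.4 | Any criterion; RECIST 1.1 where disease is measurable | Neither included nor excluded |

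The synopsis and 5.7 therefore disagree on the inputs, and 9.1.4 does not settle the matter.

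**How large the effect could be**

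The plan states no target, null rate or precision for the response proportion, so there is no figure of its own to reproduce. The illustration below takes the extreme case in which every patient alive is counted.

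Inputs:
- Background survival, Section 1.1: "PC is uniformly a terminal disease with a median survival of six months".
- Restaging at C4D14. Cycle 1 lasts 5 weeks and cycles 2 to 4 last 2 weeks each, so this is Day 35 + 14 + 14 + 14 = 77, or 76 days after Day 1. The study calendar labels it 12 weeks.
- Survival follow-up runs to one year after treatment (5.4). The last planned dose, C4D1, falls at week 5 + 2 + 2 = 9, so follow-up ends near week 9 + 52 = 61, or 427 days.
- Assumption: exponential times, S(t) = 0.5^(t / median), with 30.44 days per month and no drug effect.

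Alive with an inactive drug, median 6 months (182.6 days):
- C4D14: 0.5^(76/182.6) = 0.75. At 12 weeks it is 0.73.
- Week 61: 0.5^(427/182.6) = 0.20.

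If the true median were 9 or 12 months, the C4D14 figures would be 0.83 and 0.87. The week 61 figures would be 0.5^(427/274.0) = 0.34 and 0.5^(427/365.3) = 0.44.

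Progression-free with an inactive drug: the documents give no background PFS, so the medians here are assumptions.

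| Assumed median PFS (months) | C4D14 | Week 61 |
|---|---|---|
| 2 | 0.42 | 0.01 |
| 3 | 0.56 | 0.04 |
| 4 | 0.65 | 0.09 |
| 6 | 0.75 | 0.20 |

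At restaging the share exceeds one half only if the median is above about 2.5 to 2.8 months.

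Effect on the reported proportion: response is estimated in the per protocol population, which 9.1 does not restrict to the MTD. Its size is not fixed in advance, so the planned 12 to 24 evaluable subjects serve as a bracket. At C4D14, 0.75 × 12 = 9 and 0.75 × 24 = 18 would be counted. Exact (Clopper-Pearson) 90% intervals:
- 9/12: 0.47 to 0.93, against 0 to 0.22 for 0/12.
- 18/24: 0.57 to 0.89, against 0 to 0.12 for 0/24.

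At week 61 the expected counts are 0.20 × 12 = 2.4 and 0.20 × 24 = 4.8.

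**The case against.** The strongest answer is that the PFS/OS sentence describes group-level measures of activity, not a patient-level criterion. Section 2.3 lists tumour response, time to progression and overall survival as three separate exploratory objectives. The sentence speaks of response to therapy, whereas the marker sentence before it speaks of tumour response. The examples of response in 5.7 are all improvements or decreases. Under RECIST, as summarised in 5.7.1, a patient who has neither shrunk nor progressed has stable disease, not a response.

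Much of this stands. A reader might infer that the plan counts patients as responders for being alive or unprogressed. The documents do not say so, and most of the surrounding text points the other way. A reader might also infer a circular definition, with progression feeding PFS and PFS feeding the tumour assessment. That is not supported either: 5.7 gives progression its own criteria (clinical progression, a 20% increase on imaging, a 20% increase in marker), and PFS is not one of them. Nor can one say that most patients would qualify with an inactive drug. That holds for being alive at restaging, but not at the end of survival follow-up, and for non-progression it depends on an assumed median.

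The group-level reading does not remove the problem. After naming PFS and OS, 5.7 says that patients will be followed by a composite of the endpoints above, which may differ from patient to patient. Section 9.1.4 makes the method specific to each individual and accepts any criterion. The examples of response are not a closed list, and RECIST governs only patients with measurable disease. No sentence excludes survival or non-progression.

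**Conclusion.** The point holds as a conflict in wording that leaves the responder definition open. Section 5.7 names PFS and OS as inputs to a physician-judged response, the synopsis omits them, and 9.1.4 counts response under any criterion. The plan permits a prognosis-driven responder but does not prescribe one.

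The 75% alive at C4D14 is an upper-end figure. It rests on the protocol's six-month median, exponential survival and every living patient being counted. With trial closure read as the end of one-year follow-up, the same assumptions give about 20%. The non-progression figures rest wholly on assumed medians.

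The consequence is limited to interpreting the response proportion. Section 9.1.4 calls these analyses exploratory, 9.1.1 makes all analyses descriptive, and no dose or stopping rule uses the response rate. The toxicity and MTD conclusions are unaffected.

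**What to change.** - In 5.7, remove clinical endpoints from the list of response inputs, and move the sentence on PFS and OS to 9.1.4 as separate time-to-event summaries. Define both there: 9.1.4 currently defines only time to progression, with deaths censored, and Section 9 sets out neither PFS nor an OS analysis.
- In 9.1.4, state that responder status rests on change from baseline in lesions, markers or clinical features, and that survival or absence of progression alone is not response. Say what trial closure means for this endpoint, and correct the cross-reference from 5.6 to 5.7.

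The synopsis composite can stay as it is with respect to PFS and OS, since 5.7 would then agree with it. The cost is a few sentences of protocol text, with no new data or visits. The downside is that the reported response proportion may be lower.
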